## **7. Data collection**

### **7.1. Database**

All quantitative data will be collected electronically in face-to-face and remote interviews with trained Kenyan research assistants. We will use CommCare (Dimagi, Cambridge, USA), an electronic data collection platform, to collect the quantitative data and will upload this data to CommCare's secure server daily. A team of data experts in both Partners in Health and Research Development (PHRD) and Seattle (Fred Hutch) will monitor the data as it is coming in, and Seattle team will generate weekly data quality reports that will be shared with the PHRD team for review and feedback.

### **7.2. Participant identifiers**

Participant identification numbers have the following format: 53-XX-YYY-Z, **Table 7.**

**Table 7. Overview of participant identifiers in the Peer PrEP cRCT**

Code	Definition
53	PHRD site code
XX	Specifies participant group: 

• 03 = Index peer

• 04 = Referred peer

YYY	Sequential digits, specific to participant groups:
Z	Check digit, a random number: 1-9

## **8. Statistical considerations**

### **8.1. Analysis sets**

Data sets. Data sets for analysis will be produced by [name] and [name]. They will be .dta or .csv files containing a single header line whose variable names match those coded in CommCare. All missing values will be coded using "999". Codes for categorical variables (e.g., 0 for "No" and 1 for "Yes") will be used instead of character strings whenever possible.

**Data codebook.** A detailed codebook will be prepared, containing for each variable the form from which the variable derived, the text of the question, and all possible values for that variable with their coding. All codes and character strings representing categorical factors will be defined in the codebook.

## **9. Interim monitoring**

The study will be monitored by a Data Scientific and Monitoring Board (DSMB) approximately every six months. The project coordinators (RM, AR, NW) and statistician (CC) will generate both an open and closed report (statistician only) that will be shared with the DSMB prior to the meeting. The DSMB will give recommendations based on the report and accompanying presentation, and all recommendations and meeting minutes will be reported to the UW and Kenyan IRBs.

## **10. Data analysis**

### ***10.1. Baseline characteristics***

Baseline characteristics will be described by study group and population (e.g., index peers and referred peers). These will include demographics (e.g., gender, age, educational level), sexual behaviors (e.g., condom use), and behaviors associated with HIV risk, among other relevant characteristics.

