786 [Control arm]: Informal peer PrEP referral (n=40 peer providers). Peer providers randomized to this

[figure not shown]
787 control arm will be encouraged to refer 4 peers that they perceive to be at HIV risk and would be interested
 788 in daily oral PrEP through free public PrEP services. This control arm will include informal conversations
 789 about PrEP with peers (as per the standard of care) and delivery of a PrEP referral card (**Table 7 and**
 790 **Figure 7**):

- 791 • **Informal PrEP conversations.** Peer providers in this arm will not receive any formalized training on
 792 PrEP or HIVST and will not receive any HIVST kits for distribution to peers. They will be encouraged
 793 to talk with their peers about PrEP in the way that feels most comfortable to them and in way they
 794 would typically have conversations about new products (e.g., lipstick) or things that interest them.
- 795 • **PrEP referral card.** This control arm will also include the delivery of a PrEP referral card by peer
 796 providers to peer clients. This will be the same referral card as that delivered to peer clients in the
 797 intervention arm, with information of nearby public clinics with free PrEP services. This referral card
 798 will also contain the study phone number so peer clients remember to ping the study counselor when
 799 these informal conversations occur and to support peer clients that wish to go to another facility for
 800 PrEP support.

801 Like in the intervention arm, peer providers randomized to this arm will be encouraged to disclose PrEP
 802 use to peers, although this is not required. No WhatsApp group will be available in this arm.

803

804 **Fig. 7. Study procedures for intervention, and standard of care groups.**

[figure not shown]

805

806
 807
 808

809 **Data Collection**

811 **Overview.** **Fig. 8** highlights a timeline of study visits and
 812 data collection activities for this trial. There are two data
 813 collection time points in this study: Month 0 (peer
 814 provider baseline questionnaire) and at Month 3 (peer
 815 provider follow-up questionnaire and peer client follow-
 816 up questionnaire). After providing informed consent, all
 817 peer providers enrolled in the trial will complete a
 818 baseline (Month 0) and follow-up (Month 3) survey.
 819 Additionally, all peer clients who voluntarily provide their

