 820 contact information directly to the study team and request to be enrolled in the study will be contacted to
 821 schedule an interview at Month 3. The peer client will be screened for eligibility and consented prior to
 822 completing a follow-up survey at Month 3. This timeline will provide recruited peer clients with the
 823 opportunity to enroll in PrEP (approx. 1 month following the baseline survey) and return to healthcare
 824 facilities for one PrEP refill (approx. 3 months following the baseline survey). Sociodemographic
 825 information will be collected at baseline among peer providers and follow-up among peer clients (i.e.,
 826 their first research visit). At all follow-up visits, we will measure both self-reported outcomes related to
 827 adoption of PrEP services, as well as process-level outcomes (e.g., number of HIVST kits received in the
 828 intervention arm, PrEP referral cards received in both arms), and implementation outcomes (e.g.,
 829 intervention acceptability, appropriateness, fidelity, satisfaction).

Fig. 8. Timeline for the Aim 3 randomized trial.

831 **Setting.** Experienced quantitative researchers will collect electronic data using CommCare (Dimagi,
 832 Cambridge, USA), an electronic data collection tool, in questionnaires at baseline (Month 0) and follow-
 833 up (Month 3). While we will encourage all enrolled peer clients to come to the PHRD research site to
 834 complete the questionnaires in person, we will additionally allow for the option of questionnaire
 835 participation/completion over the phone to allow for easier engagement in follow-up activities (in
 836 particular, peer clients that might have been recruited outside of Kiambu County). Peer providers will
 837 need to come in-person to the clinic during baseline to receive the intervention they are randomized to.
 838 All participants will receive 300 KES (~\$2.70 USD) for their time and effort completing each study
 839 visit/questionnaire. For participants completing questionnaires remotely via the phone, we will send this
 840 reimbursement via a secured mobile money platform (i.e., M-Pesa), as we have done routinely for other
 841 projects. For participants that come to the PHRD research site to complete these visits/questionnaires in
 842 person, we will additionally provide reimbursement for transportation.

843 **DBS samples.** At follow-up (Month 3) DBS samples will be collected from peer clients to validate PrEP

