1014 We have extensively considered the risk of social harms related to both PrEP use and peer referral to
1015 PrEP as well as peer HIVST delivery including risks of depression/anxiety and disclosure and stigma.
1016 Our extensive experience with longitudinal follow-up of heterosexual HIV sero-discordant couples and
1017 women at risk mitigates some of this risk, and we found very little risk of social harms or anxiety related
1018 to HIV self-testing from our ongoing Pharmacy PrEP study. Analyses of social harm related to peer PrEP
1019 referral + HIVST will be by relationship status and employment status/type, given the potential for
1020 differential employment and relationship risks. In the event of a clinical need (e.g., side effects, symptoms
1021 of a sexually transmitted infection), participants will be referred to nearby HIV clinics for care.

1022 **HUMAN SUBJECTS CONSIDERATIONS**

1023 The protocol, informed consent forms (for pilot participation, for focus group discussions, and for the
 1024 randomization trial), and patient education and recruitment materials will be reviewed and approved by
 1025 the institutional review boards at the Fred Hutchinson Cancer Center and the Scientific Ethics Review
 1026 Unit (SERU) at the Kenya Medical Research Institute (KEMRI). All participants will provide informed
 1027 consent before participation in the pilot study and randomization trial. Participants will be informed of the
 1028 purpose of the study, the procedures to be followed and the risks and benefits of their participation. The
 1029 consents forms will be translated into Kiswahili. Specifically, the participants will be informed that this
 1030 novel study will answer critical questions on acceptability, feasibility, and facilitators/barriers to a model
 1031 of peer PrEP referral + HIVST among AGYW in Kenya.

1032 **Study oversight**

1033 This study will be subject to oversight by an independent Data Safety Monitoring Committee that will
 1034 periodically review data from the study, including study execution, adherence, HIV incidence, PrEP side
 1035 effects, SAEs, and social harms by study arm. Adverse events (AEs) include any forms of verbal (e.g.,
 1036 yelling, fighting), physical (e.g., hitting), emotional (e.g., depression) or economic (e.g., job loss) abuse.
 1037 While serious adverse events (SAEs) include hospitalization (for any condition, including those outside

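### For referred peers, the changeable items that SAP 10.1 calls baseline, and the status variables used to stratify social harm, can first be recorded only at Month 3, after the intervention, the outcome period and any harm

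*SAP*

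**What the plan says.** The Protocol's peer providers and peer clients are the SAP's index peers and referred peers; the SAP terms are used here.

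- **SAP 10.1 (Baseline characteristics):** "Baseline characteristics will be described by study group and population (e.g., index peers and referred peers". The content is spelled out: "These will include demographics (e.g., gender, age, educational level), sexual behaviors (e.g., condom use), and behaviors associated with HIV risk".
- **Protocol, Aim 2, Data Collection, Overview:** Month 0 is a questionnaire for index peers only; Month 3 covers both populations. On sociodemographic data: "information will be collected at baseline among peer providers and follow-up among peer clients (i.e". The Protocol explains that follow-up is the referred peers' first research visit. They are also screened and consented then.
- **SAP 6.1 (Randomization):** referred peers are chosen by index peers who have already been randomized.
- **SAP Table 1 (Follow-up):** a referred peer's three months run from the date on which staff receive her contact details. SAP Table 2 allows the index peer to supply those details at her own follow-up.
- **Protocol, Social harm considerations:** analyses of social harm related to peer PrEP "referral + HIVST will be by relationship status and employment status/type, given the potential for" differential risks.
- **Protocol, Study oversight:** adverse events include verbal abuse and others: "yelling, fighting), physical (e.g., hitting), emotional (e.g., depression) or economic (e.g., job loss) abuse". The Risks section also names problems with sexual partners.
- **SAP 10.2:** the effect models contain study group and an index-peer random effect, and no baseline covariate.
- **SAP 10.5:** adverse events are reported by randomization group and severity, with no relationship or employment strata.

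**The concern.** A baseline table by arm lets the reader judge whether the groups were alike before the intervention could act. For referred peers nothing is recorded before it acts. By Month 3 the enhanced arm has had the formal conversation, the brochure and the self-test kits, and women in both arms may have started PrEP. Any of these may change condom use or risk behaviour. An arm difference in "sexual behaviors (e.g., condom use), and behaviors associated with HIV risk" would then mix three things: an effect of the intervention, the choice of peers by index peers who know their arm, and differences in who could be reached. A reader who sees the word baseline would take it for chance imbalance.

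The social-harm strata raise a similar problem. If a referred peer loses her job or her partner because of the referral and is classified by her Month 3 status, the harm helps to decide her stratum. Harm among women who were employed or partnered when referred would then be understated, and harm in the other stratum overstated.

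**Working it through.** **1. Timing, by population**

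| Item | Index peers | Referred peers |
|---|---|---|
| First questionnaire | Month 0 | Month 3 |
| Before the intervention? | Yes | No |
| Before the outcome period and any harm? | Yes | No |
| Age, gender, education | Month 0 | Month 3, but fixed or nearly so |
| Condom use, risk behaviour | Month 0 | Month 3, changeable |
| Relationship, employment | Month 0, if among the sociodemographic items | Month 3 at the earliest |

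The Protocol does not list the sociodemographic items, so the Month 0 entry for relationship and employment is an inference. The Month 3 entry is not, because referred peers have no earlier questionnaire. Their recruitment call only leaves contact details. If the index peer supplies the details at her own follow-up, the SAP's clock puts the measurement later still.

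**2. Number of women concerned**

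SAP Table 1 gives 80 index peers and up to 320 referred peers: 320/(80 + 320) = 80% of participants have no pre-intervention record. At the planned 75% referral the figure is 240/(80 + 240) = 75%. These count women referred. The number reached may be lower, as the SAP itself warns.

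**3. The plan's own figure**

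Step 4 borrows the SAP 5.1 initiation rates, 63% and 80%, so these were checked first. With 40 clusters of 3 and ICC 0.05, the design effect is 1 + (3 − 1) × 0.05 = 1.10 and the effective size per arm is 120/1.10 = 109.1. A two-sided 5% test with pooled variance then has 79.9% power, against 80% stated. It reproduces. Nothing in this point changes the power.

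**4. Apparent baseline difference in condom use (illustration)**

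Assume that condom use was equal in both arms at referral, that a net fraction *c* of PrEP initiators change it before Month 3, and that only initiators change.

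Apparent arm difference = (80 − 63) × *c* = 17*c* percentage points.

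| *c* (assumed) | Apparent difference, points |
|---|---|
| 5% | 0.85 |
| 10% | 1.7 |
| 20% | 3.4 |
| 30% | 5.1 |

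**5. Social-harm strata (illustration)**

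Assume that half of referred peers are employed at referral, that harm risk *h* is the same in employed and not employed women, and that a fraction *q* of harmed employed women lose their job before Month 3.

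- Recorded risk, employed: *h*(1 − *q*)/(1 − *hq*)
- Recorded risk, not employed: *h*(1 + *q*)/(1 + *hq*)
- The true risk ratio is 1.0. For *h* = 5%, *q* = 25% the recorded risks are 3.80% and 6.17%, a ratio of 1.63.

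| *h* | *q* = 10% | *q* = 25% | *q* = 50% |
|---|---|---|---|
| 2% | 1.22 | 1.65 | 2.94 |
| 5% | 1.21 | 1.63 | 2.85 |
| 10% | 1.20 | 1.59 | 2.71 |

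**6. A count example, when the strata truly differ**

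Take 60 employed and 60 not employed women at referral, with 6 harms (10%) and 3 harms (5%) (assumed). Move the women whose harm was job loss:

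| Moved | Employed | Not employed |
|---|---|---|
| 0 | 6/60 = 10.0% | 3/60 = 5.0% |
| 1 | 5/59 = 8.5% | 4/61 = 6.6% |
| 2 | 4/58 = 6.9% | 5/62 = 8.1% |
| 3 | 3/57 = 5.3% | 6/63 = 9.5% |

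The direction survives one move and reverses from two.

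**The case against.** The strongest reply is that little depends on these variables. SAP 10.1 is descriptive and plans no balance test. The Protocol discloses when referred peers' data are collected. No model adjusts for the variables, and the primary outcome is reported by index peers. All of this stands. A reader might infer that the primary effect estimate is biased; the documents do not support that.

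A reader might also infer that the whole referred-peer table is compromised. It is not. Age and gender cannot be consequences of the intervention, and education hardly can over three months.

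A third tempting inference is that every social-harm stratum is affected. Index peers also report harms and have a Month 0 visit, so the problem is confined to referred peers. Even there, harassment, disclosure or suicidal thoughts need not change a woman's employment or relationship status.

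Two further replies have force. The questionnaires are not in the documents, so the Month 3 items may ask about the time of referral, although neither document says so. And the strata appear in one Protocol sentence only. SAP 10.5 does not carry them, and job loss is not among the events it lists for comparison, though it could enter the total adverse-event count. These points limit the reach of the concern but do not remove it. The Protocol's stratified analysis is still planned, and without a rule on timing Month 3 status is what an analyst would have to hand.

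**Conclusion.** The point holds for referred peers, in two places. First, condom use and HIV-risk behaviours described as baseline in SAP 10.1 are post-referral measurements in the women reached, and an arm difference in them is not evidence of baseline imbalance. Second, if the Protocol's social-harm strata use Month 3 relationship and employment status, harms that change status can place a woman in the wrong stratum.

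The timing follows directly from the documents. The sizes do not: 0.85 to 5.1 points for condom use and an apparent risk ratio of about 1.2 to 2.9 rest on the assumed values shown, and the actual distortion is unknown. It would be absereduced to nothing if the items were asked as of referral. A reader of the count example might conclude that the harm analysis will point the wrong way; it shows only that this can happen. The consequence is for what may be said about balance and about who is harmed, not for the primary result.

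**What to change.** 1. **SAP 10.1.** Limit the word baseline, and any statement about balance, to index peers at Month 0. Put referred peers in a separate table titled *Characteristics at Month 3 of referred peers reached*, with the behavioural items marked as post-referral.
2. **Social-harm strata (Protocol, Social harm considerations).** Use Month 0 status for index peers. For referred peers use relationship and employment status at the time of referral, if it was asked or can still be asked. Otherwise do not stratify their harms by Month 3 status. Write this rule into SAP 10.5, which is silent on the strata.

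The cost is a few lines of SAP text and, if collection is still open, the rewording of a few items. It may not be open: the SAP records a change approved in November 2023, six months into the trial, and cites 2025 software. The fallback of not stratifying needs no new data. The downside is some error in recalled status, or the loss of the stratified harm description for referred peers. No sample-size or power figure changes.

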### ***10.2. Effect size estimation***

Our main analysis will evaluate the difference in proportion of PrEP initiation between referred peers in the enhanced and standard groups, as reported by index peers at Month 3. Secondarily, among referred peers at Month 3, we will evaluate the difference in proportions for recent HIV testing (since referral) and PrEP continuation (i.e., PrEP refilling) and median difference for self-reported PrEP adherence (using 100-point validated scale).

Our analysis is prespecified as intention to treat (ITT), using complete-case information and standard errors clustered at the level of the peer provider. We will estimate risk differences (RD) with 95% confidence intervals (CI) for binary outcomes using mixed-effect models with Gaussian distributions, identity links, study group fixed effects, and index peer random effects to adjust for clustering. For continuous outcomes, we will estimate median differences (MDs) using linear quantile mixed methods with the same specifications as those described above.

All the analyses will consider an alpha level of 0.05 as significant and will be run in R Studio (RStudio: Integrated Development Environment for R. Posit Software, MA 2025).

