Implementation outcomes. Additionally, in all follow-up surveys among peer providers and clients we will measure a number of implementation outcomes including participants' perceptions of the intervention's

882 acceptability, feasibility, and appropriateness. To measure these outcomes, we will use validated scales
 883 and established theories/frameworks adapted to the Kenyan setting and to young women (e.g., the
 884 Theoretical Framework of Acceptability). Additionally, at follow-up, we will have peer clients complete a
 885 checklist of materials received from peer providers to measure “fidelity” of the intervention in both
 886 intervention arms.

887 Costs are another important implementation outcome we plan on measuring during this trial. To measure
 888 costs, we will micro-cost the formal delivery model and compare the incremental cost of this model with
 889 the existing informal referral strategy (Objective 4). Activity-based micro-costing will be conducted for
 890 costs incurred (e.g., HIVST kits) and costs averted (e.g., personnel). We will use time and motion studies
 891 to measure staff time spent training peer providers. Estimates of cost using the activity-based approach
 892 will be compared with the top-down approach (i.e., the budget divided by the number of peer providers
 893 and peer clients)^{74 75 76 77} (**Table 9**).

894 **Safety.** We will measure “safety” of the intervention by
 895 screening for PrEP side effects (i.e., nausea, vomiting,
 896 headache) among peer clients (and as reported by both peer
 897 provider and clients) and any reports of social harm (e.g.,
 898 physical, verbal, emotional violence) related to our delivery
 899 model (Objective 4).

Table 9. Description of costing inputs

Costs: Start-up: microplanning, training, mobilization;

Recurrent: personnel, capital, supplies, overhead

Data: Project budget; time & motion; staff interviews;
published literature; central price list & salaries

Unit cost: Cost/PrEP users trained, peer referred, peer
initiated on PrEP, peer retained on PrEP.

900 The findings from this trial (described above) will be used to inform a NIH R01 proposal for a peer PrEP
 901 referral + HIVST community-randomized trial and budget impact analysis.

902 *Statistical analysis*

[figure not shown]
903 We will measure effect size estimates using mixed effects multilevel regression models (primary

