## 3. Study overview and objectives

### 3.1. Study overview

**Table 1. Overview of the Peer PrEP cRCT components**

[figure not shown]
Protocol title:	Peer PrEP referral + HIV self-test delivery for PrEP initiation among young Kenyan women: randomized implementation trial
Short title:	Peer PrEP Study
Design:	This study is a hybrid effectiveness-implementation randomized trial
Population:	We will enroll two different population types in this study: 1. Index peers : (Also called PrEP users or peer providers in our formative research and pilot study). Adolescent girls and young women ≥16-24 years  old using PrEP for at least one month in the past 12 months.

	
2. Referred peers: (Also called peers or PrEP clients in our formative research and pilot study). Female peers <math>\geq 16</math>-24 years old of the index peer whom the index peer thinks has behaviors associated with HIV risk and may be interested in and benefit from daily oral PrEP.
 
16- and 17-year-olds must be emancipated minors; all participants must be able and willing to provide informed consent.

Randomization:	1:1 enhanced group: standard group

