#### **5. Sample size justification**

##### **5.1. Sample size calculation**

If we assume that index peers refer 75% of suggested referred peers, this leaves us with three clients per peer provider, or 240 referred peers in total. We performed power calculations for our primary outcome, the proportion of referred peers who initiated PrEP at three months, in Stata 16.1 using methods for cluster-randomized trials (cRCTs), where each cluster is a peer group of one index peer and three referred peers.

**Table 6** and **Figure 3** shows the power we attain to detect various increases in the proportion of referred peers who initiated PrEP in the enhanced group versus the standard. For our power calculations, we assumed 40 clusters (index peers) per group, 3 sampling units (referred peers) per cluster, and an intra-cluster correlation coefficient (ICC) of 0.05, which is standard for cRCTs, we might have 80% power to detect a difference of 17% PrEP initiators between the enhanced group (80%) and standard group (63%).

**Figure 3. Power calculation to detect increase in the percentage of referred peers initiating PrEP in the enhanced group compared to the standard.**

**Table 6. Increase in the % of referred peers initiating PrEP in the enhanced group compared to standard under different assumptions.**

Power	Standard: % PrEP initiation	Enhanced: % PrEP initiation	% increase
80%	57.1%	75.0%	17.7%
	63.0%	80.0%	17.0%
	69.1%	85.0%	15.7%
85%	55.8%	75.0%	19.2%
	61.7%	80.0%	18.3%
	67.9%	85.0%	17.10%
90%	54.2%	75.0%	20.8%
	60.1%	80.0%	19.9%
	66.4%	85.0%	18.7%

Assumptions: ICC: 0.05; clusters (providers) per arm: 40; units (clients) per cluster: 3 (75% of suggested clients referred)

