## 6. Randomization and masking

## **6.1. Randomization**

Randomization list. A Fred Hutch statistician will prepare a list of randomization assignments for index peers with block sizes of 4. This list will be stored in a password-protected electronic file on a Fred Hutch server.

Randomization implementation. Index peers will be randomized at enrollment, which will occur at Month 0. Then, referred peers will be chosen by index peers. At the time of randomization, index peers will open an opaque randomization envelope, given to them by a study research assistant, that has their study arm assignment inside.

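### Index-peer PrEP continuation is analysed without its own baseline value; one prespecified covariate would recover some precision on this secondary outcome

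*SAP*

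**What the plan says.** - **Outcome models.** SAP 10.2 gives binary outcomes a Gaussian, identity-link mixed model with "identity links, study group fixed effects, and index peer random effects to adjust for clustering". The adherence score is analysed by "linear quantile mixed methods with the same specifications as those described above", so it has no covariate either. The Protocol (Statistical analysis) says "We will measure effect size estimates using mixed effects multilevel regression models (primary" and names study arm as the primary predictor; it lists no other.
- **Sensitivity analyses.** None of the six in SAP 10.4 adjusts for a baseline variable.
- **Baseline data.** SAP 10.1: "Baseline characteristics will be described by study group and population". No further use is stated.
- **Randomisation.** SAP Table 1 gives "1:1 enhanced group: standard group". SAP 6.1 describes a "list of randomization assignments for index peers with block sizes of 4". Neither document states a stratification factor.
- **Who is randomised.** SAP Table 1 describes index peers as "using PrEP for at least one month in the past 12 months". SAP Table 2 and Protocol Table 6 require only that PrEP has at some time been dispensed. Either wording admits women who are no longer refilling.
- **The outcome concerned.** SAP Table 3 lists, as a secondary outcome, the share of index peers who refilled PrEP in the past 3 months. The text of SAP 10.2 mentions continuation only among referred peers, so the model for index peers is left to inference.

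**The concern.** Refill behaviour before enrolment is the baseline version of refill behaviour at Month 3, and one would expect the two to be related. With 80 index peers and no stratification, the arms can differ by chance in the share already lapsed. An unadjusted comparison carries that variation as noise.

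At stake is the precision of one secondary outcome that is already imprecise. There is also a question of timing. If the baseline table shows an imbalance and someone then wishes to adjust, SAP section 1 would require that analysis to be labelled unplanned. A covariate named in advance avoids that.

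**Working it through.** **1. The plan's own figure.** SAP 5.1: "we assumed 40 clusters (index peers) per group, 3 sampling units (referred peers) per cluster, and an intra-cluster correlation coefficient (ICC) of 0.05", with 63% versus 80% at 80% power.
- Design effect: 1 + (3 − 1) × 0.05 = 1.10. Effective n per arm: 120 / 1.10 = 109.1.
- Pooled z-test, two-sided 0.05: z = [0.17 × √109.1 − 1.96 × √(2 × 0.715 × 0.285)] / √(0.63 × 0.37 + 0.80 × 0.20) = (1.776 − 1.251) / 0.627 = 0.84, so power is 79.85%.

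The stated 80% therefore reproduces without any covariate, and the sample size does not rely on adjustment.

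**2. Index-peer continuation: inputs.** From the documents: 40 index peers per arm, one observation each. Assumed, because the documents give no value: lapsed share q of 10% or 30%, and a refill rate of 70% among current users against 20% or 40% among lapsed users (gap of 50 or 30 points).

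**3. Gain from one covariate.** With marginal refill rate p, the share of variance explained is q(1 − q) × gap² / [p(1 − p)]. Estimating one coefficient in 80 units inflates the variance by about 77/76 = 1.013.

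| Lapsed | Gap (points) | p | Share explained | Variance ratio, adjusted/unadjusted |
|---|---|---|---|---|
| 30% | 50 | 0.55 | 0.0525 / 0.2475 = 21.2% | 0.788 × 1.013 = 0.80 |
| 10% | 50 | 0.65 | 0.0225 / 0.2275 = 9.9% | 0.901 × 1.013 = 0.91 |
| 30% | 30 | 0.61 | 0.0189 / 0.2379 = 7.9% | 0.921 × 1.013 = 0.93 |
| 10% | 30 | 0.67 | 0.0081 / 0.2211 = 3.7% | 0.963 × 1.013 = 0.976 |
| any | 0 | – | 0% | 1.013 |

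Simulated trials of 40 + 40 in blocks of 4 agree (0.80, 0.91, 0.93, 0.975 and 1.01). The variance cut is thus about 2.5% to 20%, with a cost of about 1% if the covariate is useless. In the most favourable row the standard deviation of the risk difference falls from √(2 × 0.2475 / 40) = 11.1 points to 11.1 × √0.80 = 9.9 points, equivalent to 80 / 0.80 = 100 index peers instead of 80.

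**4. Chance imbalance is not a second harm.** At 30% lapsed, the between-arm difference in lapsed share has SD √(2 × 0.21 / 40) = 10.2 points. Times a 50-point gap, this moves the estimate by 5.1 points. But (5.1 / 11.1)² = 21%, the same share as in the first row. The imbalance is already inside the 11.1 points and hence inside the unadjusted interval.

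**5. Validity of the unadjusted estimate.** In simulation its mean lay within 0.003 of the true difference, with type I error between 5.2% and 6.2%.

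**6. Primary outcome.** An index-peer covariate can remove only between-cluster variance. The cluster-mean variance is proportional to 0.05 + 0.95/3 = 0.367, of which 0.05 (13.6%) is between clusters. If the covariate explains 10%, 25% or 50% of that part, power goes from 79.85% to 80.4%, 81.2% or 82.6%. The ceiling, at 100%, is 85.4%. These figures ignore the cost of estimation.

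A fuller covariate set (prior refill, age and two indicators for three counties) inflates the variance by about 77/73 = 1.055. If prior refill explains half of the between-cluster part and the others nothing, the ratio is (0.342 / 0.367) × 1.055 = 0.98; at 25% it is (0.354 / 0.367) × 1.055 = 1.02, a net loss.

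**The case against.** The strongest reply is that leaving out covariates is a legitimate choice. Index peers are randomised, so the comparison is unbiased and the interval covers chance imbalance (steps 4 and 5). This stands in full. A reader might infer from the missing covariates that the results would be biased or that an imbalance would go uncorrected in some harmful sense. The documents do not support that reading.

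Second, a reader might infer that every model, including the primary, should be adjusted. Nothing in the documents links an index peer's refill history to PrEP initiation by her friends, and at the planned ICC the gain is small and can turn into a loss with several covariates (step 6). This also stands.

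Third, it is tempting to say that PrEP status at Month 0 must be known. Enrolment establishes only that PrEP was dispensed, which is true of every index peer and so carries no information. Recency is not named as a Month 0 item for the trial: Protocol Table 3, which lists PrEP use at Month 0, belongs to the pilot, and the trial's Data Collection section names only sociodemographic information at baseline. This stands as a condition on the fix.

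Fourth, the lapsed share may be low. The Protocol describes providers as young women using PrEP and recruits them largely through clinics that deliver it. At 10% lapsed the gain is 2.5% to 9%, which is small but still exceeds the 1% cost of a useless covariate.

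**Conclusion.** The point holds as a modest matter of efficiency on one secondary outcome. Index-peer continuation is analysed without its baseline value, and a single covariate would cut its variance by about 2.5% to 20%, or cost about 1% if not predictive. The range rests on an assumed lapsed share (10% to 30%) and refill gap (30 to 50 points), which the sponsor can replace with its own data. The outcome has little precision to spare: with 40 per arm, power for 50% versus 70% is 44.5%, rising to 46.1%, 51.3% or 56.0% if the covariate's correlation with the outcome is 0.2, 0.4 or 0.5 (the table's rows correspond to 0.19 to 0.46).

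No change to the main analysis of the primary outcome follows. Its stated power is correct without adjustment and would realistically rise only to between 80% and 83%.

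**What to change.** 1. **Confirm the data.** Check whether the Month 0 eligibility check or questionnaire recorded if the index peer was dispensed PrEP in the 3 months before enrolment. If it did not, the change cannot be made and the unadjusted analysis stands.
2. **Amend SAP 10.2 before unblinding.** State the model for index-peer continuation and include that one yes/no variable as a fixed effect, with the unadjusted estimate shown beside it. The same sentence should drop the index-peer random effect for this outcome, because one observation per index peer cannot identify it.
3. **Leave the referred-peer models as they are.** Keep the unadjusted estimate as main for the primary and other referred-peer outcomes. An adjusted estimate there is at most a sensitivity analysis in SAP 10.4.
4. **Do not adjust for referred-peer characteristics.** They are first measured at Month 3, after randomisation and after index peers have chosen whom to refer.

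The cost is one sentence in the SAP and one degree of freedom, and the change depends on the variable having been recorded.
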